## Discussion

Regarding nearly all the symptoms analysed in the clinical trial, there was a mild to significant improvement. The largest improvement of an average of 2.6 points was discovered in symptoms related to insomnia and anger outbursts. It can be hypothesised that due to increased rest and relaxation, patients were able to manage their negative emotions more efficiently.

Positive results were also found within the patients' own value of life. Large improvements were found in a patients' perception of overall happiness, satisfaction and fulfilment, as well as general quality of life. All these values increased by a score of 2 or more on average. It is evident that the PEMF treatment is beneficial in providing patients with a relaxing and calm therapy which in turn helps appreciation for quality of life, and motivation in facing daily tasks head on.

Physical symptoms were also improved using PEMF therapy. Issues relating to headaches, fatigue, and flashbacks were all reduced over the course of the trial. Patients reported feeling more relaxed, and physical pains has subsided (See 'Patient Four' below).

It is important to note that the only symptom that experienced no average change was depression. It can be postulated that this is due to depression being a more deep-rooted issue which was prevalent for an extended period prior to the clinical trial. It is promising to see that cases of depression were not worsened during the trial, indicating that PEMF therapy is able to improve symptoms related to depression (fatigue, insomnia, anger). Nonetheless, the lack of change in depression forms a consideration for future clinical trials (see 'Considerations').

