## Study Summary

Title	Pulsed ElectroMagnetic Field (PEMF) therapy in Treating Post-Traumatic Stress Disorder (PTSD) & Trauma
Methodology	Single arm observing treatment intervention; no control, no placebo/sham
Study Duration	Estimated duration for the main protocol (the start and end of the treatment programme) is approximately 3 weeks
Study Centre(s)	Private clinic in Bristol, U.K.
Objectives	
Primary Objective: To evaluate the efficacy of Artificial Intelligence (AI) guided software rendering PEMF treatment to treat PTSD & Trauma
 
Secondary Objective: To evaluate the feasibility of AI implementation in drastically reducing the time required to train PEMF therapists, thereby allowing faster adoption of PEMF therapy into mainstream practice through use by other licensed/regulated/trained healthcare professionals such as talking therapists, nurses, doctors, social workers, and carers

Number of Actual Participants	5
Diagnosis and Main Inclusion Criteria	
Inclusion Criteria:
 
 
• Aged 18 or over
 
• Have been diagnosed with PTSD or Trauma
 
• Have been experiencing on-going, continuous symptoms of PTSD or Trauma for at least the past 6 months
 
• Can attend 6 sessions lasting 90 minutes over 3 weeks
 
• Consent and Compliance with all requirements of clinical trial, including dissemination of results, with anonymity of identity provided
 
 
Exclusion Criteria:
 
 
• Under the age of 18 years old
 
• Have not been diagnosed with PTSD or Trauma
 
• Have serious health conditions such as cancer
 
• Unable to attend 6 sessions
 

Study Product, Dose, Route, Regimen	Treatment group will receive 6 sessions, each lasting 1.5 hours of PEMF treatment over the course of 3 weeks through the CE-marked CIO devices

	classified by the U.S. Food & Drug Administration as a Type 11a Medical Device. SCIO devices contain a frequency generator and scanning technology, along with electrode harnesses that connect to the forehead, wrists, and ankles. The devices are controlled by software that is guided by A.I.
Statistical Methodology	Primary Endpoint: Symptoms of PTSD & Trauma are evaluated through a questionnaire, with scale ratings for different symptoms. Symptoms were correlated with information available on the NHS website.

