## **Methods:**

### **Study Design:**

Single-arm study involving five (5) subjects undergoing 6 90-minute sessions of Pulsed Electromagnetic Therapy. All patients received the same treatment. Harnesses were placed on the head, wrists, and ankles of the body to conduct the electromagnetic frequencies. Patients were encouraged to rest and relax whilst the therapy was conducted, as it does not require any tasks by the patient. Patients were required to complete a questionnaire before and after the trial. This questionnaire enquired about the different symptoms related to PTSD and Trauma, and asked patients to rate their symptoms on a scale. These questionnaires would form the foundation of the study's findings, as it would give a clear comparison of symptoms before and after the trial.

All aspects of the trial were exempt from a U.K. ethics committee board review because the trial was a non-invasive method of treatment, did not collect and tissue or fluid samples and the device is CE-marked and had been used in other trials previously approved and published on Clinical Trials.gov. Documents were provided on clinicaltrials.gov as evidence of this exemption.

All patients were from the inclusion criteria, and any patients exhibiting cases from our exclusion list were rejected from the pilot study. Patients were recruited through the National Centre for Electromagnetic Therapy social media pages, including Facebook, Instagram, and [www.ncet.co.uk](http://www.ncet.co.uk).

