## Results & Findings

### **Prior to the Trial**

Once participants had been screened and approved for clinical trial study, they were required to fill out a questionnaire that sought to establish the specific issues that they were experiencing due to PTSD and Trauma. These responses were weighted as an average and are provided below.

For clarification, a rating of one (1) on the scale indicates a very severe case of a specific symptom, five (5) means a frequent feeling of a symptom, and ten (10) indicates that the symptom is not experienced at all. A weighted average score has been chosen as a foundation for our results, to compare them more accurately before and after the trial. However, specific notes and observations shall be included where needed.

Statements were also used, whereupon a patient would respond with either Daily (3 or more times a week), Weekly (2 to 3 times a week), Monthly (3 to 4 times a month), or Rarely (Once every 3 months or longer).

Question	Average Score
Have you experienced or witnessed a life-changing event that caused intense fear, hopelessness or horror?	All patients recorded 'Yes'.
Have you experienced either repeating dreams, flashbacks, or intense physical/emotional stress that relate back to the	Daily – 1 Patient Monthly – 2 Patients Rarely – 2 Patients

traumatic event(s)?	
Do you avoid thoughts, feelings, actions, conversations, or people related to the event?	Daily – 1 Patient Weekly – 2 Patients Monthly – 1 Patient Rarely – 1 Patient
Have you felt detached or negative towards yourself or others since the traumatic event(s) happened?	Daily – 4 Patients Monthly – 1 Patient
Do you have problems sleeping?	Daily – 1 Patient Weekly – 2 Patients Rarely – 2 Patients
Do you become increasingly irritable, angry, or engage in self-destructive behaviour?	Daily – 1 Patient Monthly – 3 Patients Rarely – 1 Patient
How long have your symptoms persisted?	Longer Than Three Years – 3 Patients Longer Than A Year – 1 Patient 8-12 Months – 1 Patient
Do you experience heightened version of anxiety, sensitivity, or depression?	Daily – 3 Patients Weekly – 1 Patient Monthly – 1 Patient
Rate Your Quality of Life	Average Score: 6
Rate The Severity of Depression	Average Score: 6.4
Rate How Difficult It Is To Fall Asleep	Average Score: 5.6
Rate The Severity of Flashbacks Relating to a Traumatic Event	Average Score: 5
Rate The Severity of Headaches or 'Brain Fog'	Average Score: 4.6
Rate The Severity of Fatigue	Average Score: 5

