### **During The Trial**

There were no changes to the initial plan for the clinical trial. All patients attended their arranged appointments and reported no negative side effects to the treatment.

The Lead Practitioner noted valuable verbal feedback during sessions with each patient.

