### After The Trial

Once the trial had been completed over the course of 3 weeks, patients were asked to complete the same questionnaire that was sent out prior to the clinical trial. In the table below, responses have been recorded as an average, with a percentage comparison of improvement or decline in symptoms.

Question	Average Score
Have you experienced or witnessed a life-changing event that caused intense fear, hopelessness or horror?	All patients recorded 'Yes'.
Rate Your Quality of Life	Average Score: 8 ( Improvement of >2 points )
Rate The Severity of Depression	Average Score: 6.4 ( No change )
Rate How Difficult It Is To Fall Asleep	Average Score: 8.2 ( Improvement of >2.6 points )
Rate The Severity of Flashbacks Relating to a Traumatic Event	Average Score: 7.4 ( Improvement of >2.4 points )
Rate The Severity of Headaches or 'Brain Fog'	Average Score: 6 ( Improvement of >1.4 points )
Rate The Severity of Fatigue	Average Score: 6.8 ( Improvement of >1.8 points )
Rate The Severity of Anger or Irritable Outbursts	Average Score: 7.4 ( Improvement of >2.6 points )

Rate How Difficult It Is To Complete Daily Tasks	Average Score: 7.4 ( Improvement of >1.6 points )
Rate The Severity of Your Anxiety	Average Score: 7 ( Improvement of >0.8 points )
Rate Your Level of Overall Happiness	Average Score: 8.2 ( Improvement of >2 points )
Rate Your Level of Satisfaction and Fulfilment In Life	Average Score: 7.8 ( Improvement of >2 points )

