## **Reflections and Considerations**

The clinical trial highlights the many benefits of PEMF therapy in treating symptoms related to PTSD and Trauma. All patients felt a significant improvement in their lives and indicated a wish to continue with PEMF therapy after the clinical trial had concluded. It can also be suggested that taking the time out of a daily schedule to attend PEMF therapy allows a patient to relax and rest. This form of meditation can be hypothesised as a beneficial side effect to PEMF therapy.

It should also be noted that patients with previous experience with Cognitive Behavioural Therapy (CBT) were more receptive to treatment, especially within the first two sessions. This is due to the selected patients (two of the five patients in the study) being able to communicate their triggers and emotions more clearly to the Lead Practitioner during PEMF treatment. This allowed the patients to experience a form of CBT with the clinical trial staff, whilst providing them time to relax out of their regular schedule. These two patients especially saw an improvement with sleeping, indicating that the opportunity to vocalise their symptoms and emotions helped them alleviate PTSD-related problems.

Whilst the clinical trial was a success in achieving the primary objective, there are numerous considerations and reflections for further clinical trials into PEMF therapy.

- A larger study would be beneficial in further analysing the benefits of PEMF therapy in treating PTSD and Trauma. Access to a larger cohort of volunteers, with a larger time frame of more PEMF sessions would produce a larger result pool. This would also allow for a control group, a treatment group, and a sham group to compare results more accurately and draw wider conclusions to the specific benefits of PEMF treatment.
- Twice weekly sessions proved to be tiring for patients (see Patient Three's statement above), therefore a longer, more spaced-out study would allow patients to recover from PEMF treatment before their subsequent sessions. This would remove the risk of exhausting the patients which may hamper accurate results of the study.
- This study was restricted due to financial and time restraints. Staff numbers were restricted to the Lead Practitioner and a Research Assistant to disseminate results. The financial impact of conducting a clinical trial for free dictated that the trial would be short to make it viable for the sponsor's funding.

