It is of the opinion of the National Centre of Electromagnetic Therapies that this clinical trial was a success in meeting its primary objective in improvement symptoms related to PTSD and Trauma through PEMF. The clinical trial has highlighted the many benefits of PEMF treatment. Nearly all studied symptoms improved for all patients during the trial, and there was no worsening of symptoms recorded. The evidence provided within this document attests to these conclusions.

Therefore, it is recommended that further clinical trials into the development of Pulsed Electromagnetic Therapy as treatment for symptoms of PTSD and Trauma should be conducted. It is our goal to conduct a similar study on a far larger scale, with more participants and a longer trial period. This conclusion has been reached due to the promising positive benefits of PEMF therapy shown through this clinical trial. The clinical trial also concludes that PEMF therapy is a beneficial, non-invasive alternative to prescription medication in relation to PTSD and Trauma. Whilst the results cannot claim to be representative of the entire U.K., the clinical trial has indicated that there are significant benefits to Bio-Resonance treatment and should therefore be studied further.

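### The conclusion claims significant benefits, yet the available text has no test, measure of spread or threshold for meaningful change, and with five patients a two-sided distribution-free paired test cannot fall below p = 0.0625

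*Combined protocol and SAP*

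**What the plan says.** The Statistical Methodology row of the Study Summary gives the primary endpoint as "Symptoms of PTSD & Trauma are evaluated through a questionnaire, with scale ratings for different symptoms". It names no test, significance level, sidedness or sample-size reasoning. Study Design describes a "Single-arm study involving five (5) subjects undergoing 6 90-minute sessions of Pulsed Electromagnetic Therapy". Under Prior to the Trial the analysis is a comparison of averages: "A weighted average score has been chosen as a foundation for our results, to compare them more accurately before and after the trial". After The Trial says that "responses have been recorded as an average, with a percentage comparison of improvement or decline in symptoms", and its table prints a mean and a change in points for each of 11 rated items. It gives no standard deviation, confidence interval or p-value.

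The word *significant* then describes the results in three places:

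- Discussion: "Regarding nearly all the symptoms analysed in the clinical trial, there was a mild to significant improvement".
- Reflections and Considerations: "All patients felt a significant improvement in their lives".
- The closing text of that section: "the clinical trial has indicated that there are significant benefits to Bio-Resonance treatment".

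**The concern.** In a trial report, a conclusion of significant benefits is easily read as saying that chance has been addressed. Nothing in the available text addresses it. If the word is meant in its everyday sense, it is still undefined: no boundary separates a mild change from a significant one, and no minimum meaningful change is stated for any item.

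What is at stake is the headline conclusion. The same closing text presents the therapy as a beneficial alternative to prescription medication, so a reader may give the result more evidential weight than five uncontrolled before-after pairs can carry.

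**Working it through.** **Inputs.** There are five patients (Study Design). No missed sessions are reported: "All patients attended their arranged appointments and reported no negative side effects to the treatment". Each item therefore has at most five pairs. Ratings run from 1 to 10, higher being better (Prior to the Trial). Whole-number ratings are assumed; every printed average is a multiple of 0.2, as that implies with n = 5. A two-sided 5% level is assumed as a benchmark, since the document sets none.

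**Step 1: reproduce the printed changes.** Change = average in After The Trial minus average in Prior to the Trial. Total = 5 × change. The last column is used in Step 3.

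| Item | Before | After | Change | Total over 5 patients | SD of change below which paired t gives p < 0.05 |
|---|---|---|---|---|---|
| Quality of life | 6.0 | 8.0 | 2.0 | 10 | 1.61 |
| Depression | 6.4 | 6.4 | 0.0 | 0 | none |
| Falling asleep | 5.6 | 8.2 | 2.6 | 13 | 2.09 |
| Flashbacks | 5.0 | 7.4 | 2.4 | 12 | 1.93 |
| Headaches or brain fog | 4.6 | 6.0 | 1.4 | 7 | 1.13 |
| Fatigue | 5.0 | 6.8 | 1.8 | 9 | 1.45 |
| Anger | 4.8 | 7.4 | 2.6 | 13 | 2.09 |
| Daily tasks | 5.8 | 7.4 | 1.6 | 8 | 1.29 |
| Anxiety | 6.2 | 7.0 | 0.8 | 4 | 0.64 |
| Happiness | 6.2 | 8.2 | 2.0 | 10 | 1.61 |
| Satisfaction | 5.8 | 7.8 | 2.0 | 10 | 1.61 |

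All 11 printed changes reproduce.

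**Step 2: smallest attainable exact p-value.** With n pairs, the sign, signed-rank and sign-flip tests share the floor 2 × (1/2)^n two-sided and (1/2)^n one-sided.

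- n = 5, two-sided: 2/32 = 0.0625.
- n = 5, one-sided: 1/32 = 0.03125.
- n = 6, two-sided: 2/64 = 0.03125, so six pairs are the fewest that can reach two-sided 5%.

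Enumerating every set of five whole-number changes that gives each printed mean, the smallest two-sided sign-flip p-value is:

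- 0.0625 on nine items.
- 0.125 on anxiety. A total of 4 points cannot come from five patients who each gained at least 1, so the best case is four improved and one unchanged: 2/16 = 0.125.
- 1.0 on depression (the sign test's minimum there is 0.375).

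**Step 3: paired t-test.** On 4 degrees of freedom the critical value is 2.776, so p < 0.05 needs SD of change < mean change × √5 / 2.776. For 2.6 points this is 2.6 × 2.236 / 2.776 = 2.09; for 2.0 points, 1.61; for 0.8 points, 0.64. No SD or patient-level score appears in the available text, so whether any item meets its limit cannot be determined.

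Anxiety shows how much depends on the missing detail. If no patient worsened, five patterns sum to 4: (4,0,0,0,0), (3,1,0,0,0), (2,2,0,0,0), (2,1,1,0,0) and (1,1,1,1,0). Only the last passes: SD = 0.447, t = 0.8 / (0.447/2.236) = 4.0, p = 0.016.

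**The case against.** The strongest reply is that the word mostly describes size. In the Discussion its opposite is *mild*, not *non-significant*, and the sentences that follow give point changes. In Reflections, the statement about what patients felt reports their perception and may rest on patient accounts that are not in the text available here. Both arguments stand. A reader might infer that all three uses are claims of statistical significance; only the one in the closing text reads plausibly as a conclusion about effect. Nor does *significant* cover changes from 0.8 to 2.6 points: that range belongs to the Discussion's whole phrase, from mild upwards.

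A second reply is that the benchmark is imported. The document sets no level or sidedness, and Expected Outcomes anticipates improvement in every patient, which would suit a one-sided test. This also stands in part. A reader might infer that no test could reach 5% with five patients. That is wrong: a one-sided exact test or a paired t-test could. Neither was prespecified, however, and the t-test relies on approximate normality of changes in five bounded ratings.

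A third reply is that little depends on the word. A reader might infer that the recommendation for further trials rests on it. The closing text also grounds that recommendation on promising positive results and says the results are not representative of the U.K., while Reflections calls for a larger study with control and sham groups. The recommendation would survive without the adjective.

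What remains is that the closing conclusion asserts significant benefits with neither an inferential basis nor a stated descriptive threshold.

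**Conclusion.** The point holds for the closing conclusion and, more weakly, for the Discussion. The available text plans and reports no test, SD, interval or threshold for meaningful change. With five pairs, a two-sided distribution-free paired test has a floor of 0.0625 on every item. The item-specific minima (0.0625 on nine items, 0.125 on anxiety, 1.0 on depression for the sign-flip test) also assume whole-number ratings.

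The result depends on the two-sided 5% benchmark and on restricting the tests to distribution-free ones. It does not show that the changes are due to chance, or that every analysis would fail. Nor would a small p-value attribute the change to the treatment, because there is no control group. The absence of a test is established only for the text available here, which lacks the figures and some of the patient accounts.

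Severity is moderate to minor. This is a wording correction in a completed pilot, and descriptive reporting without a test is defensible at n = 5. It does not make the reported means unusable; all of them reproduce.

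**What to change.** 1. In the closing text of Reflections and Considerations, replace *significant* with the observed size, for example: mean change 0.0 to 2.6 points on 11 items, n = 5, uncontrolled, no hypothesis test.
2. For consistency, make the same replacement in the Discussion's opening sentence; the item-level figures are already in the After The Trial table.
3. In Reflections, make clear that the sentence about improvement in patients' lives is their own report.

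No test has to be added. If an inferential word is kept, it should rest on a named test of the five pairs for each item, labelled post hoc, with the two-sided exact floor of 0.0625 and the number of items examined (11) stated beside it.

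The cost is an edit to three sentences, with no new data. The downside for the sponsor is that the conclusion reads less favourably.

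### Depression (0) and anxiety (+0.8) changed least of the 11 ratings, yet the visible Discussion leaves out anxiety and the report declares its primary objective met without naming either result

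*Combined protocol and SAP*

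**What the plan says.** The design is a "Single-arm study involving five (5) subjects undergoing 6 90-minute sessions of Pulsed Electromagnetic Therapy", with no control. The Study Summary makes the primary endpoint a symptom questionnaire with scale ratings. No section gives a rule for deciding that the primary objective was met. On the scale, 1 is very severe and "ten (10) indicates that the symptom is not experienced at all", so a rise is an improvement.

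At baseline (Prior to the Trial), one joint question on anxiety, sensitivity or depression was answered "Daily – 3 Patients Weekly – 1 Patient Monthly – 1 Patient". The question on feeling detached or negative was answered "Daily – 4 Patients Monthly – 1 Patient".

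The After The Trial table gives 11 mean ratings with their changes. The row "Rate The Severity of Your Anxiety" shows a gain of 0.8 and the depression row shows none. The section says that the same questionnaire was completed again, but it reports no frequency answers.

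The Discussion opens with "Regarding nearly all the symptoms analysed in the clinical trial, there was a mild to significant improvement" and gives a paragraph to the lack of change in depression. Reflections and Considerations says "Whilst the clinical trial was a success in achieving the primary objective", and the closing paragraphs say "this clinical trial was a success in meeting its primary objective". Those paragraphs add that almost every symptom studied got better in every patient and that none was recorded as getting worse.

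**The concern.** The trial asks whether the treatment relieves PTSD and trauma symptoms. With no success criterion, the verdict on the primary objective rests on which results the text takes up. The Discussion touches on ten of the eleven rated items; the one absent from the visible text is anxiety, the smallest non-zero change. Depression is reported, but its unchanged mean is read as encouraging, and neither result reaches the conclusion.

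The closing claim about every patient goes further than the table. Only group means appear in the text, and Expected Outcomes had anticipated at least a marginal improvement in all patients, so the patient-level statement matters. These conclusions support a recommendation for larger trials and a description of the treatment as an alternative to prescription medication. A reader of the closing text alone would not learn that two core mental-health ratings moved little or not at all.

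**Working it through.** **Step 1: reproduce the reported changes.** Inputs are the means in the Prior to the Trial and After The Trial tables. Change = after − before; room = 10 − before; share = change / room. The share assumes that 10 is also the best score on the three well-being items.

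| Item | Before | After | Change | Room | Share |
|---|---|---|---|---|---|
| Depression | 6.4 | 6.4 | 0 | 3.6 | 0% |
| Anxiety | 6.2 | 7.0 | 0.8 | 3.8 | 21% |
| Headaches / brain fog | 4.6 | 6.0 | 1.4 | 5.4 | 26% |
| Daily tasks | 5.8 | 7.4 | 1.6 | 4.2 | 38% |
| Fatigue | 5.0 | 6.8 | 1.8 | 5.0 | 36% |
| Quality of life | 6.0 | 8.0 | 2.0 | 4.0 | 50% |
| Happiness | 6.2 | 8.2 | 2.0 | 3.8 | 53% |
| Satisfaction | 5.8 | 7.8 | 2.0 | 4.2 | 48% |
| Flashbacks | 5.0 | 7.4 | 2.4 | 5.0 | 48% |
| Falling asleep | 5.6 | 8.2 | 2.6 | 4.4 | 59% |
| Anger | 4.8 | 7.4 | 2.6 | 5.2 | 50% |

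All 11 printed changes reproduce. Ten of eleven means rose. The nine items other than depression and anxiety average (1.4 + 1.6 + 1.8 + 2.0 + 2.0 + 2.0 + 2.4 + 2.6 + 2.6) / 9 = 18.4 / 9 = 2.04.

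**Step 2: is it limited room to improve?** Depression and anxiety started among the best-rated items, so this needs checking. They are still lowest as a share of the room left (0% and 21%, against 26% to 59%). Happiness started at the same 6.2 as anxiety and rose 2.0. Limited room does not explain the ranking.

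**Step 3: what the means imply for individuals.** The report calls its averages weighted but gives no weights. Every printed mean is a multiple of 0.2, which fits plain means of five whole-number ratings, and I assume that.

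- Depression: 5 × 6.4 = 32 before and 32 after. The five changes sum to zero, so either nobody changed or at least one patient worsened and offset another's gain. The means cannot say which.
- Anxiety: 5 × 6.2 = 31 before and 5 × 7.0 = 35 after, a gain of 4 points. One patient could supply all of it: a baseline mean of 6.2 implies at least one rating of 6 or lower, which leaves 4 points to the top. If all five had improved by at least 1 point, the gain would be at least 5, so at least one patient did not improve.

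**Step 4: what the text takes up.** The Discussion touches on falling asleep, anger, quality of life, happiness, satisfaction, daily tasks, headaches, fatigue, flashbacks and depression. Anxiety does not appear there, in the Reflections or in the closing paragraphs.

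**The case against.** The opening sentence of the Discussion is literally correct: ten of eleven means rose, and mild is a fair word for 0.8. The anxiety figure is printed in the results table, and the depression result has its own paragraph. Nothing is concealed; the fault is in the interpretation. Daily tasks, too, are mentioned only in passing and without a score. Some text following the Discussion is missing from the public copy, so the absence of anxiety is established only for the visible text. All of this stands, and it limits the point to the narrative and the conclusion.

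A reader might go further and infer that the treatment worked least on the complaints most patients had daily, and most on complaints few had. The documents do not support that:

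- The commonest daily complaint, feeling detached or negative (four of five), has no rating and no reported follow-up, so its change is unknown.
- The three-of-five figure comes from one question that joins three complaints with an or. It does not show daily anxiety, or daily depression, in three patients.
- Trouble falling asleep shares the largest gain, yet the report says that all patients had a sleep problem, and three of five had one at least weekly (daily 1, weekly 2). The daily and weekly bands also overlap at three times a week.
- On the rating scale itself, depression (6.4) and anxiety (6.2) were the mildest of the eight symptom ratings at baseline.
- Quality of life, happiness and satisfaction each rose 2.0 and have no frequency question.

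**Conclusion.** The point holds as a fault of selective interpretation. Depression (0) and anxiety (+0.8) are the two smallest of 11 mean changes, well below the 2.04 average of the other nine. The visible Discussion passes over anxiety, and the conclusion declares the primary objective met without naming either result. The statements about every patient and about no worsening are not supported by the group means. They are not shown to be false either: the wording allows exceptions among the symptoms, and the individual scores might bear it out for the rest.

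The arithmetic on changes rests only on the printed means. The statements about individuals assume plain means of whole-number ratings. With five patients, no standard deviations and no control, the ranking of items is descriptive. It does not establish that anxiety and depression respond less than other symptoms, and it gives no ground for tying the size of a change to how many patients had the complaint daily.

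**What to change.** In the Discussion, replace the opening sentence with: *Ten of eleven mean ratings rose, by 0.8 to 2.6 points; anxiety (+0.8) and depression (0) changed least, and no follow-up is reported for feeling detached or negative, which four of five patients reported daily at baseline.* If the frequency answers were collected again, report them and drop the last clause.

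In Reflections and Considerations and in the closing paragraphs, replace the unqualified claim of success with: *Most mean ratings rose in this uncontrolled group of five, but little or no mean change was seen in anxiety and depression.* Delete the extension of the improvement to every patient and the statement that no worsening was recorded, unless the individual before and after scores support them.

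The cost is rewording from figures already reported and, if the patient-level claims are to stay, a look at the five sets of ratings. The downside for the sponsor is a less favourable stated conclusion.

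### The Discussion credits PEMF with an evident benefit through relaxation, but rest was encouraged for every patient, relaxation was never rated, and the design cannot separate the two

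*Combined protocol and SAP*

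**What the plan says.** The primary objective in the Study Summary, Purpose and Goals sections is the efficacy of PEMF in PTSD and trauma. The Study Summary describes a single arm with no control and no placebo or sham.

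The Study Design section describes the session: "Patients were encouraged to rest and relax whilst the therapy was conducted, as it does not require any tasks by the patient". It adds: "All patients received the same treatment".

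The Discussion reports gains in happiness, fulfilment and quality of life ("All these values increased by a score of 2 or more on average") and then concludes: "It is evident that the PEMF treatment is beneficial in providing patients with a relaxing and calm therapy". The same sentence goes on to say that this helps patients value their quality of life and motivates them for daily tasks.

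Elsewhere the document is more cautious about rest. One paragraph earlier the Discussion says: "It can be hypothesised that due to increased rest and relaxation, patients were able to manage their negative emotions more efficiently". Reflections and Considerations suggests that "taking the time out of a daily schedule to attend PEMF therapy allows a patient to relax and rest", and offers this only as a hypothesised side benefit. Both that section and the closing statement before the Endnotes nevertheless declare the primary objective met.

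**The concern.** The Discussion sentence sets out a causal chain: PEMF gives a relaxing therapy, and relaxation improves well-being and motivation. It presents the chain as established and credits it to PEMF. Yet rest belonged to the session procedure whatever the field did, and it was the same for everyone. The two intermediate steps, relaxation and motivation, were not rated.

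This is narrower than a general complaint about the missing control group. A specific companion to the device is written into the Methods and put forward by the authors as a possible source of benefit. It is then counted as evidence for the device. At stake is what the trial may say about its primary objective, because the later claims of success rely on the same attribution.

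**Working it through.** **1. Reproduce the reported changes.** Inputs are the item averages in the tables under Prior to the Trial and After The Trial. Change = after minus before; a higher score is better.

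| Item | Before | After | Change | Reported |
|---|---|---|---|---|
| Quality of life | 6.0 | 8.0 | +2.0 | 2 |
| Depression | 6.4 | 6.4 | 0 | none |
| Falling asleep | 5.6 | 8.2 | +2.6 | 2.6 |
| Flashbacks | 5.0 | 7.4 | +2.4 | 2.4 |
| Headaches or brain fog | 4.6 | 6.0 | +1.4 | 1.4 |
| Fatigue | 5.0 | 6.8 | +1.8 | 1.8 |
| Anger | 4.8 | 7.4 | +2.6 | 2.6 |
| Daily tasks | 5.8 | 7.4 | +1.6 | 1.6 |
| Anxiety | 6.2 | 7.0 | +0.8 | 0.8 |
| Happiness | 6.2 | 8.2 | +2.0 | 2 |
| Satisfaction and fulfilment | 5.8 | 7.8 | +2.0 | 2 |

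All 11 differences reproduce, including the three gains of 2.0 that lead into the sentence.

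**2. Look for the steps in the chain.** The after-trial survey in the Illustrations lists the same 11 items (2.1 to 2.11).
- Items rating relaxation: 0 of 11.
- Items rating motivation: 0 of 11. The nearest is difficulty with daily tasks, which is a different question.
- Relaxation appears in the Discussion only as a narrative remark, with no score and no before-and-after comparison.

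**3. Look for a contrast between device and rest.** By the Study Design section, all five patients had the same treatment and the same encouragement to rest.
- Patients who rested without PEMF: 0 of 5.
- Patients who had PEMF without encouragement to rest: 0 of 5.

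Each observed change is therefore a single total: PEMF effect + effect of rest + other change over the three weeks. With one group, only the total is observed. A gain of 2.0 could be all device, all rest, or any mixture, and nothing in the data narrows the split. Reflections and Considerations adds another component that cannot be separated: for two of the five patients it describes something like talking therapy with staff.

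**4. Precision of the totals.** No standard deviation is reported, so this step rests on assumed values. The 95% half-width is t(0.975; 4 df) × SD/√5, with t = 2.776.
- SD of change 1: 2.776 × 1/2.236 = 1.2 points
- SD of change 2: 2.5 points
- SD of change 3: 3.7 points

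For an SD of 2 or more, a gain of 2.0 would not be clearly distinguished from no change, even before asking what caused it. The main point does not depend on this step.

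**5. Set the statements side by side.** The benefit delivered through a relaxing therapy is called evident and is assigned to PEMF in one Discussion sentence. In the preceding paragraph, rest and relaxation are only a hypothesis. In Reflections and Considerations, time away from the daily schedule is what allows the rest, again as a hypothesis. The certainty of the first statement has no source in the other two or in the data.

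**The case against.** **The sentence does not rest on relaxation alone.** It directly follows three repeated ratings that rose by 2.0 each. This is correct and must be granted. It does not rescue the attribution, because those ratings are the uncontrolled totals of step 3.

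**The design is disclosed.** The Study Summary states that there is no control or sham, and Reflections and Considerations proposes both for a later study and raises rest as a contributor. This is to the authors' credit, but neither statement corrects a sentence that calls the benefit evident and assigns it to PEMF.

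**Stronger readings that the documents do not support:**
- *The same conclusion would have been reached with an inert device.* That depends on how far rest alone moves the ratings, which the documents do not give. As an illustration, assume no PEMF effect, n = 5, an SD of change of 2, and normal changes correlated at 0.3 to 0.6 across items. If rest added 1 point, the chance of all three averages reaching 2 or more is only about 0.01 to 0.03. The supportable claim is that the device and the rest cannot be told apart.
- *The authors explain their largest gains, falling asleep and anger, by session rest.* The Discussion offers rest as the reason negative emotions were better managed. Coming straight after insomnia, it may mean better sleep rather than rest during sessions.
- *Relaxing contradicts tiring.* The text says "Twice weekly sessions proved to be tiring for patients". That concerns the twice-weekly schedule, and a calm session can belong to a tiring schedule.
- *Rest was an instruction.* The Study Design section says encouraged, which is softer.

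**Conclusion.** The concern holds in this form: the Discussion's claim of an evident PEMF benefit through relaxation is not supported by the design or the data. Rest was encouraged for all five patients, none of the 11 repeated ratings measures relaxation or motivation, and there was no comparison group. The three gains of 2.0 that precede the sentence, and the 1.6 on daily tasks to which it alludes, are correctly calculated but cannot be divided between PEMF and scheduled rest.

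The size is one of attribution: the share of each gain due to the device is not identified, and no reported figure changes. The conclusion assumes only that the encouragement to rest applied in all sessions, which is the plain reading of the Study Design section. It does not say that PEMF has no effect, nor that rest produced the gains.

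**What to change.** In the Discussion, replace the sentence that begins by calling the benefit evident with wording such as:

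> Rest was encouraged in every session, and neither relaxation nor motivation was rated before and after treatment. The average gains in quality of life, happiness, fulfilment and daily tasks are uncontrolled changes in five patients. They may reflect scheduled rest and cannot be credited to PEMF.

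Qualify the statements of success in Reflections and Considerations and in the closing statement before the Endnotes in the same way, so that they report uncontrolled before-and-after changes and do not present PEMF efficacy as shown.

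The cost is a few sentences and a less favourable conclusion. No new data or analysis is needed.
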